This study is a multi-dose, randomized, open-label clinical trial to evaluate the efficacy, safety, and PK/PD profile of SR604 in patients with von Willebrand disease. The screening period is 28 days, extendable up to 42 days. The study includes 4 groups: 0.2 mg/kg Q4W, 0.4 mg/kg Q4W, 0.4 mg/kg Q6W, and 0.4 mg/kg Q8W, with a planned enrollment of 6 patients per group, totaling 24 patients. The treatment period is 24 weeks, with Q4W, Q6W, and Q8W dosing intervals corresponding to 6, 4, and 3 doses, respectively. The extended treatment period is no longer than 24 weeks, with Q4W, Q6W, and Q8W dosing intervals allowing a maximum of 6, 4, and 3 additional doses, respectively. The last visit of the extended treatment period is completed at 28, 42, or 56 days after the last dose for Q4W, Q6W, and Q8W dosing intervals, respectively. The follow-up period for Q4W, Q6W, and Q8W dosing intervals extends to 84 days after the last dose.

Inclusion Criteria:

Patients must meet ALL of the following inclusion criteria to be enrolled:

1. Age ≥ 18 years and ≤ 65 years at the time of signing informed consent, regardless of sex;
2. At screening, patients with a confirmed diagnosis of von Willebrand disease (VWD) with documented evidence and a defined VWD subtype;
3. At least 4 new bleeding episodes within 6 months prior to screening;
4. No active bleeding symptoms prior to the first dose;
5. The subject or impartial witness fully understands and is able to comply with the protocol requirements, is willing to complete the study as planned, and voluntarily agrees to provide biological samples for testing as required by the protocol; is able to understand the procedures and methods of this clinical trial, provides voluntary participation after full informed consent, and personally signs the informed consent form.

Exclusion Criteria:

Patients meeting ANY of the following exclusion criteria will not be enrolled:

1. Known history of hypersensitivity to the investigational drug formulation or any of its components;
2. Intolerance to subcutaneous injection or presence of other local skin abnormalities or dermatological conditions that may affect drug administration and safety assessment;
3. Meeting any of the following criteria at screening:
 - a. Hemoglobin < 60 g/L;
 - b. Platelet count $< 80 \times 10^9$ /L;

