treatment period, and a maximum of 6, 4, or 3 additional doses administered during the extended treatment period, respectively. Specific dosing details are described in the dosage and administration section. Patients will undergo efficacy and safety assessments according to the visit schedule, along with PK/PD blood sample collection.

When bleeding occurs during the treatment period requiring treatment, the occurrence and management of bleeding events will be documented.

The investigator will select appropriate treatment medications and measures based on the patient's specific condition, including desmopressin (DDAVP), plasma-derived VWF-containing factor VIII concentrate or plasma-derived/recombinant VWF preparations, cryoprecipitate or fresh plasma, antifibrinolytic agents, sex hormones, and topical thrombin or fibrin glue for bleeding management, or other hemostatic agents as deemed appropriate for the patient's condition.

Follow-up Period:

From the last dose until study exit, if bleeding events occur, the investigator will select appropriate treatment medications and measures based on the patient's specific condition, including desmopressin (DDAVP), plasma-derived VWF-containing factor VIII concentrate or plasma-derived/recombinant VWF preparations, etc.

At Day 84 after the last dose or upon early withdrawal at any time, the investigator will perform safety assessments including vital signs, physical examination, adverse event assessment, laboratory tests (complete blood count, urinalysis, and blood chemistry), coagulation function, FDP, 12-lead ECG, anti-SR604 antibodies (ADA), and neutralizing antibodies. Bleeding events and their treatment, adverse events, and concomitant medications/non-drug therapies will also be recorded. If safety evaluation parameters are abnormal, follow-up must continue until values return to normal, become abnormal but not clinically significant, stabilize, or return to baseline.

Pharmacokinetics/Pharmacodynamics (PK/PD)

Biological Sample Collection:

All patients participating in this study are required to provide biological samples at designated time points for PK/PD analysis, according to the planned sampling time points (see tables below).

Biological sample collection will be performed by authorized or trained medical personnel according to the requirements of the testing facility.

Table 7-2 PK/PD Sampling Time Points and Time Windows for 0.2 mg/kg Q4W

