Collection Time Point	Time Label	PK Sample	PD Sample	Tolerance Window
First Dose	D1 (predose)	▲	▲	Within 1 h predose
	D2 (24 h postdose)	▲	▲	± 4 h
	D3 (48 h postdose)	▲	▲	± 4 h
	D5 (96 h postdose)	▲	▲	± 4 h
	D8 (168 h postdose)	▲	▲	± 4 h
	D11 (240 h postdose)	▲	▲	± 4 h
	D15 (336 h postdose)	▲	▲	± 4 h
2nd Dose	D29 ± 2 d (672 h after first dose)	▲	▲	Within 1 h predose
3rd Dose	D57 ± 2 d (within 1 h predose)	▲	▲	Within 1 h predose
4th Dose	D85 ± 2 d (within 1 h predose)	▲	▲	Within 1 h predose
	24 h postdose	▲	▲	± 4 h
	48 h postdose	▲	▲	± 4 h
	96 h postdose	▲	▲	± 4 h
	168 h postdose	▲	▲	± 4 h
	240 h postdose	▲	▲	± 4 h
	336 h postdose	▲	▲	± 4 h
5th Dose	D113 ± 2 d (672 h after 4th dose)	▲	▲	Within 1 h predose
6th Dose	D141 ± 2 d (predose)	▲	▲	Within 1 h predose
7th Dose*	D169 ± 2 d (predose)	▲	▲	Within 1 h predose
8th Dose*	D197 ± 2 d (predose)	▲	▲	Within 1 h predose
9th Dose*	D225 ± 2 d (predose)	▲	▲	Within 1 h predose
10th Dose*	D253 ± 2 d (predose)	▲	▲	Within 1 h predose
11th Dose*	D281 ± 2 d (predose)	▲	▲	Within 1 h predose
Last Dose	672 h postdose	▲	▲	± 2 d
	1008 h postdose	▲	▲	± 2 d
	1344 h postdose	▲	▲	± 2 d
	1680 h postdose	▲	▲	± 2 d
	2016 h postdose	▲	▲	± 3 d

* Collected depending on actual duration of treatment.

If duplicate blood collection time points occur, collect only once.

Table 7-3 PK/PD Sampling Time Points and Time Windows for 0.4 mg/kg Q4W

Collection Time Point	Time Label	PK Sample	PD Sample	Tolerance Window
First Dose	D1 (Pre-dose)	▲	▲	Within 1h pre-dose
	D11 (240h post-dose)	▲	▲	±4h
2nd Dose	D29±2d (Pre-dose)	▲	▲	Within 1h pre-dose
3rd Dose	D57±2d (Pre-dose)	▲	▲	Within 1h pre-dose
4th Dose	D85±2d (Pre-dose)	▲	▲	Within 1h pre-dose
5th Dose	D113±2d (Pre-dose)	▲	▲	Within 1h pre-dose
6th Dose	D141±2d (Pre-dose)	▲	▲	Within 1h pre-dose
7th Dose※	D169±2d (Pre-dose)	▲	▲	Within 1h pre-dose
8th Dose※	D197±2d (Pre-dose)	▲	▲	Within 1h pre-dose
9th Dose※	D225±2d (Pre-dose)	▲	▲	Within 1h pre-dose
10th Dose※	D253±2d (Pre-dose)	▲	▲	Within 1h pre-dose
11th Dose※	D281±2d (Pre-dose)	▲	▲	Within 1h pre-dose
Last Dose	Pre-dose	▲	▲	Within 1h pre-dose
	240h post-dose	▲	▲	±4h

※ Collected based on actual dosing duration.

If duplicate sampling points exist, collect only once.

Table 7-4 PK/PD Sampling Time Points and Time Windows for 0.4 mg/kg Q6W

Collection Time Point	Time Label	PK Sample	PD Sample	Tolerance Window
First Dose	D1 (Pre-dose)	▲	▲	Within 1h pre-dose
	D11 (240h post-dose)	▲	▲	±4h
2nd Dose	D43±2d (Pre-dose)	▲	▲	Within 1h pre-dose

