3rd Dose	D85±2d (Pre-dose)	▲	▲	Within 1h pre-dose
4th Dose	D127±2d (Pre-dose)	▲	▲	Within 1h pre-dose
5th Dose※	D169±2d (Pre-dose)	▲	▲	Within 1h pre-dose
6th Dose※	D211±2d (Pre-dose)	▲	▲	Within 1h pre-dose
7th Dose※	D253±2d (Pre-dose)	▲	▲	Within 1h pre-dose
Last Dose	Pre-dose	▲	▲	Within 1h pre-dose
	240h post-dose	▲	▲	±4h

※ Collected based on actual dosing duration.

If duplicate sampling points exist, collect only once.

Table 7-5 PK/PD Sampling Time Points and Time Windows for 0.4 mg/kg Q8W

Collection Time Point	Time Label	PK Sample	PD Sample	Tolerance Window
First Dose	D1 (Pre-dose)	▲	▲	Within 1h pre-dose
	D2 (24h post-dose)	▲	▲	±4h
	D3 (48h post-dose)	▲	▲	±4h
	D5 (96h post-dose)	▲	▲	±4h
	D8 (168h post-dose)	▲	▲	±4h
	D11 (240h post-dose)	▲	▲	±4h
	D15 (336h post-dose)	▲	▲	±4h
	D29 (672h post-dose)	▲	▲	±2d
	D43 (1008h post-dose)	▲	▲	±2d
	D57±2d (1344h post-first dose)	▲	▲	Within 1h pre-dose
3rd Dose	D113±2d (Pre-dose)	▲	▲	Within 1h pre-dose
	24h post-dose	▲	▲	±4h
	48h post-dose	▲	▲	±4h
	96h post-dose	▲	▲	±4h
	168h post-dose	▲	▲	±4h
	240h post-dose	▲	▲	±4h
	336h post-dose	▲	▲	±4h
	672h post-dose	▲	▲	±2d
	1008h post-dose	▲	▲	±2d
4th Dose※	D169±2d (1344h post-3rd dose)	▲	▲	Within 1h pre-dose
5th Dose※	D225±2d (Pre-dose)	▲	▲	Within 1h pre-dose
Last Dose	672h post-dose	▲	▲	±2d
	1008h post-dose	▲	▲	±2d
	1344h post-dose	▲	▲	±2d
	1680h post-dose	▲	▲	±2d
	2016h post-dose	▲	▲	±3d

※ Collected based on actual dosing duration.

If duplicate sampling points exist, collect only once.

Note: Sampling points may be adjusted based on newly acquired data.

Note: Blood collection time points may be adjusted based on newly obtained data results.

Collected blood samples will be centrifuged and stored frozen at -60 degrees C or below. Test samples will be transported by a professional cold-chain logistics company to the central laboratory for analysis. Backup samples will be stored frozen at -60 degrees C or below at the clinical trial institution or transported by a professional cold-

chain logistics company to a third party designated by the sponsor after study completion.

Biological Sample Testing:

PK/PD biological samples collected from all patients will be shipped to the central laboratory. Specific requirements will follow the relevant standard operating procedures and testing requirements established by the central laboratory.

Efficacy Endpoints

Primary Efficacy Endpoint:

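### Tables 7-2 and 7-5 omit the predose PK/PD sample at the last dose of a full course (12th Q4W, 6th Q8W), which Tables 7-3 and 7-4 include

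*Protocol*

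**What the plan says.** **Number of doses.** Protocol, Overall Design: "The treatment period is 24 weeks, with Q4W, Q6W, and Q8W dosing intervals corresponding to 6, 4, and 3 doses, respectively". For the extension the same section continues "allowing a maximum of 6, 4, and 3 additional doses, respectively", and Study Procedures repeats the limit: "a maximum of 6, 4, or 3 additional doses administered during the extended treatment period, respectively". The maximum totals are therefore 12 (Q4W), 8 (Q6W) and 6 (Q8W).

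**Sampling tables.**
- Table 7-2 (0.2 mg/kg Q4W): the last numbered predose row is the 11th dose, "D281 ± 2 d (predose"). The Last Dose block begins at "672 h postdose" and runs to 2016 h.
- Table 7-5 (0.4 mg/kg Q8W): the last numbered predose row is the 5th dose, "D225±2d (Pre-dose"). The Last Dose block again runs from 672 h to 2016 h.
- Tables 7-3 (0.4 mg/kg Q4W) and 7-4 (0.4 mg/kg Q6W): the numbered rows stop at the 11th and 7th dose, but the next block opens with "Last Dose Pre-dose" and adds a 240 h sample.

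**Footnotes.** Starred rows are taken only if treatment lasts that long. Coinciding time points are sampled once. A general note allows time points to be changed in the light of new data. None of these adds a sample at the 12th Q4W or 6th Q8W dose.

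**The concern.** All four tables end their numbered rows one dose short of the permitted maximum. Tables 7-3 and 7-4 make this good in the Last Dose block; Tables 7-2 and 7-5 do not. In those two arms, a patient who stops early has a predose sample at the last dose, because that dose is one of the numbered rows. A patient who completes the full course does not. The protocol gives no reason for making collection depend on this, and the two arms are otherwise the intensively sampled ones, with a washout profile to 84 days.

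At stake is one late concentration and PD value per completer. The washout profile then has no level just before the dose from which it starts. Pharmacokinetics is a secondary objective, and the dose rationale rests on staying above a minimum effective concentration of 0.506 ug/mL, so late troughs are of interest. These two arms also have the lowest average dose: 0.2/4 = 0.4/8 = 0.05 mg/kg per week, against 0.4/6 = 0.067 and 0.4/4 = 0.1 in the others.

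**Working it through.** **Inputs.** Dose numbers and intervals are from Overall Design and the Efficacy Endpoints notes (28, 42 and 56 days). Sampling rows are from Tables 7-2 to 7-5. Group size is 6 ("with a planned enrollment of 6 patients per group, totaling 24 patients").

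**1. Is the full course really planned?** Dose k falls on day 1 + (k − 1) × interval. The 12th Q4W dose falls on 1 + 11 × 28 = D309. The protocol gives a maximum of about 438 days per patient. Screening 42 + last dose day 309 + follow-up 84 = 435; adding the 3-day window on the 2016 h sample gives 438. This breakdown is inferred, since the protocol does not give one, but the stated maximum agrees with a 12-dose course.

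**2. Predose rows against permitted doses (D1 included).**

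| Table | Arm | Maximum doses | Day of final dose | Last numbered predose row | Predose row in Last Dose block | Predose samples, full course |
|---|---|---|---|---|---|---|
| 7-2 | 0.2 mg/kg Q4W | 12 | 1 + 11 × 28 = D309 | 11th, D281 | no | 11 of 12 |
| 7-3 | 0.4 mg/kg Q4W | 12 | D309 | 11th, D281 | yes | 12 of 12 |
| 7-4 | 0.4 mg/kg Q6W | 8 | 1 + 7 × 42 = D295 | 7th, D253 | yes | 8 of 8 |
| 7-5 | 0.4 mg/kg Q8W | 6 | 1 + 5 × 56 = D281 | 5th, D225 | no | 5 of 6 |

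In Table 7-5 the D57 row has no separate dose label, but its predose window makes it the predose sample of the 2nd dose, and it is counted as such. The only last doses without a predose row are the 12th in Table 7-2 and the 6th in Table 7-5.

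**3. Length of the gap.**
- Q4W: the first sample after the last dose is at D309 + 28 = D337; 337 − 281 = 56 days.
- Q8W: the first sample after the last dose is at D281 + 28 = D309; 309 − 225 = 84 days.

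With a predose sample at the last dose these would split into 28 + 28 and 56 + 28 days.

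**4. Patients.** 6 + 6 = 12 of 24 at most. The extension has a maximum length only, so the number who reach the last dose is unknown.

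**5. End-of-interval troughs, full course.** Here D1 is left out as a baseline, and the sample at the end of the final interval is counted.
- Table 7-2: doses 2 to 11 plus 672 h = 11 of 12.
- Table 7-3: doses 2 to 12 = 11 of 12.
- Table 7-4: doses 2 to 8 = 7 of 8.
- Table 7-5: doses 2 to 5 plus 1344 h = 5 of 6.

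Counted this way, every arm is one trough short. Tables 7-2 and 7-5 lack the one before the last dose; Tables 7-3 and 7-4 lack the one after it.

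**The case against.** The strongest answer is that little depends on this sample.

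- A reader might infer that only these two arms lack a last-interval trough. Step 5 shows otherwise: the trough produced by the final dose is scheduled in Tables 7-2 and 7-5 (672 h or 1344 h) and not in Tables 7-3 and 7-4, which stop at 240 h. This part of the objection stands.
- A reader might infer that the arms cannot be compared at a common late time. Continuing patients have a D169 predose sample in all four arms (7th dose Q4W, 5th Q6W, 4th Q8W). A last-dose predose row would match by label only, since the final dose falls on D309, D295 or D281. This also stands.
- No listed PK parameter becomes inestimable. A predose level can be compared with the end-of-interval level at an intensively sampled dose: D85 with D113 in Table 7-2, and D113 with D169 in Table 7-5. This stands.
- A reader might infer that the final dosing visit has no PT value. PT is also in the safety coagulation panel, and the visit schedule for that panel is not in the text available, so its absence cannot be asserted.
- The tables follow a visible rich and sparse pattern, and nothing in the protocol requires a predose sample at every dose. The pattern explains why the blocks differ. It does not explain why the richly sampled arms take a predose sample at every dose except the last of a full course.

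The general permission to change sampling times does not meet the point, because it schedules nothing.

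**Conclusion.** The gap is real and follows from the tables alone. Tables 7-2 and 7-5 schedule a predose PK/PD sample at every dose except the 12th Q4W and the 6th Q8W. Each full-course completer in these arms misses one sample. The consequence is minor: what is lost is one late predose value and the level before the last dose that would anchor the washout profile, not the estimability of steady-state Cmin or the comparison across arms. The conclusion assumes that some patients receive the maximum number of doses, and that no sampling instruction outside the available text supplies the row. It is worth correcting because the sample costs almost nothing and cannot be recovered once the visit has passed.

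**What to change.** Add a PK/PD row for a predose sample, within 1 h before dosing, to the Last Dose block of Tables 7-2 and 7-5, as Tables 7-3 and 7-4 already have. Full-course predose sampling then becomes 12 of 12 and 6 of 6. The existing note on coinciding time points prevents double collection in patients whose last dose is one of the numbered rows. If the omission is intended, say so with the reason.

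The cost is a correction to two tables and one extra tube at an existing dosing visit for at most 12 patients. It should be made before the first patient reaches that visit.

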Administer by slow subcutaneous injection according to the labeled volume, completing the injection within 5 minutes, adjusting to patient comfort. Injection sites may include the thigh (mid-anterior aspect), abdomen (excluding the 5 cm radius area around the navel), or the lateral aspect of the upper arm (abdominal administration is recommended). A different injection site should be selected for each injection within a 1-month period, with

at least 2.5 cm distance from the previous injection area. Do not inject into areas that may rub against belts or waistbands. Do not inject into areas with moles, scars, or bruises. Do not inject into areas with skin tenderness, redness, induration, or broken skin.

Dosage:

Two dose levels are used in this study: 0.2 mg/kg or 0.4 mg/kg. The dose is calculated based on the patient's body weight and assigned dose group: $\text{Dose (mg)} = \text{Dose Level (mg/kg)} \times \text{Body Weight (kg)}$. Administered subcutaneously once every 4 weeks, 6 weeks, or 8 weeks, for a continuous treatment duration not exceeding 48 weeks.

The injection volume is calculated based on the labeled product specification. For injection volumes not exceeding 1 mL, the volume should be precise to 0.01 mL (rounded). For injection volumes exceeding 1 mL, the volume should be precise to 0.1 mL (rounded). For injection volumes exceeding 2.5 mL, the dose should be administered as divided injections.

Study Procedures

This study includes a screening period, treatment period, extended treatment period, and follow-up period.

Screening Period:

Patients enter the screening period after signing the informed consent form. Screening assessments and evaluations will be completed according to the visit schedule. The screening period shall not exceed 28 days (may be extended if the patient receives medication for a bleeding event, or if the 28-day screening period does not encompass one menstrual cycle for female patients of reproductive potential; however, the maximum extension shall not exceed 42 days). Patients meeting all inclusion criteria and none of the exclusion criteria will enter the study.

Treatment Period and Extended Treatment Period:

Eligible patients enter a 6-month treatment period and an extended treatment period of no more than 6 months. Dosing occurs every 4 weeks, 6 weeks, or 8 weeks according to the assigned dose group, with a total of 6, 4, or 3 doses administered during the

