Treated total annualized bleeding rate (TABR) at Week 24 of treatment and over the total treatment period (including treatment period and extended treatment period).

The treated annualized bleeding rate (ABR) at Week 24 of treatment and over the total treatment period (including treatment period and extended treatment period) shall be calculated using the following formulas:

Treated ABR at Week 24

$$= \frac{(\text{Number of treated bleeding episodes within the dosing interval after the last dose during the 24-week period}) \times 365.25}{(\text{Date of last dose within the 24-week period} - \text{Date of first dose} + \text{Dosing interval})}$$

Treated ABR over the total treatment period (including treatment period and extended treatment period)

$$= \frac{((\text{Number of treated bleeding episodes within the dosing interval after the last dose}) \times 365.25)}{((\text{Date of last dose} - \text{Date of first dose} + \text{Dosing interval}))}$$

Note: Total bleeding includes spontaneous bleeding and traumatic bleeding. Treated bleeding refers to bleeding episodes managed with corresponding pharmacotherapy.

Note: For the Q4W group, the dosing interval is 28 days; for the Q6W group, the dosing interval is 42 days; for the Q8W group, the dosing interval is 56 days.

Secondary Efficacy Endpoints:

1. Treated spontaneous annualized bleeding rate (SABR) at Week 24 of treatment and over the total treatment period (including treatment period and extended treatment period);

2. Treated traumatic annualized bleeding rate at Week 24 of treatment and over the total treatment period (including treatment period and extended treatment period);

3. Treated total, spontaneous, and traumatic annualized bleeding rates by bleeding site at Week 24 of treatment and over the total treatment period (including treatment period and extended treatment period);

4. Total annualized bleeding rate (TABR) at Week 24 of treatment and over the total treatment period (including treatment period and extended treatment period).

The total annualized bleeding rate (ABR) at Week 24 of treatment and over the total treatment period (including treatment period and extended treatment period) shall be calculated using the following formulas:

ABR at Week 24

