$$= \frac{((\text{Number of bleeding episodes within the dosing interval after the last dose during the 24 – week period}) \times 365.25)}{(\text{Date of last dose within the 24 – week period} - \text{Date of first dose} + \text{Dosing interval}))}$$

ABR over the total treatment period (including treatment period and extended treatment period)

$$= \frac{((\text{Number of bleeding episodes within the dosing interval after the last dose}) \times 365.25)}{((\text{Date of last dose} - \text{Date of first dose} + \text{Dosing interval}))}$$

Note: Total bleeding includes spontaneous bleeding and traumatic bleeding.

Note: For the Q4W group, the dosing interval is 28 days; for the Q6W group, the dosing interval is 42 days; for the Q8W group, the dosing interval is 56 days.

5. EQ-5D-5L health questionnaire utility scores at Week 24 of treatment and over the total treatment period (including treatment period and extended treatment period);

6. Change from baseline in EQ-VAS score at Week 24 of treatment and over the total treatment period (including treatment period and extended treatment period).

Exploratory Efficacy Endpoints:

1. Change from baseline in PBAC score at Week 24 of treatment and over the total treatment period (including treatment period and extended treatment period) (females with menstruation only);

2. Annualized menorrhagia bleeding rate at Week 24 of treatment and over the total treatment period (including treatment period and extended treatment period) (females with menstruation only);

3. Categorization of replacement therapeutic agents prior to investigational product administration, at Week 24 of treatment, and over the total treatment period (including treatment period and extended treatment period).

Safety Endpoints

Incidence of AEs/SAEs/AESIs assessed through clinical signs and symptoms, vital signs, physical examination, laboratory tests (complete blood count, urinalysis, and blood chemistry), coagulation function [prothrombin time (PT), thrombin time (TT), international normalized ratio (INR), fibrinogen (FIB), activated partial thromboplastin time (APTT), D-dimer], FDP, 12-lead ECG, injection site reactions, hypersensitivity/allergic reactions, thrombotic events, etc.; incidence of drug-related AEs/SAEs/AESIs; number and incidence of patients with anti-drug antibodies (ADA) and neutralizing antibodies.

Pharmacokinetic Parameters

Single-dose PK parameters:

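### As written, the primary ABR formula counts bleeds in the last dosing interval only but divides by the whole treatment time, understating ABR 3- to 6-fold at Week 24 and up to 12-fold in total

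*Protocol*

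**What the plan says.** Under Efficacy Endpoints, the protocol names treated total ABR at Week 24 and over the total treatment period as primary, and makes the formulas given there binding.

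- **Week 24 numerator:** "Number of treated bleeding episodes within the dosing interval after the last dose during the 24-week period", multiplied by 365.25.
- **Week 24 denominator:** "Date of last dose within the 24-week period", minus the date of first dose, plus the dosing interval.
- **Total-period numerator:** "Number of treated bleeding episodes within the dosing interval after the last dose", again over last dose minus first dose plus one interval.
- **Secondary endpoint 4 (all bleeds, treated or not):** the same structure at both time points, with "Number of bleeding episodes within the dosing interval after the last dose" in the total-period formula.

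A note fixes the interval length: "For the Q4W group, the dosing interval is 28 days; for the Q6W group, the dosing interval is 42 days; for the Q8W group" it is 56 days. Nothing in the protocol says that the count of bleeds starts at the first dose.

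**The concern.** An annualised rate is a count divided by the time over which the count was made. Here the count covers one dosing interval and the time covers all of them. Bleeds in every earlier interval are dropped, but the days on which they could have occurred stay in the denominator.

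Three consequences follow if the formula is programmed as written:

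- **Level.** ABR is too low in every group, so any comparison with bleeding before the study leans towards benefit.
- **Ranking.** The share of time counted depends on the dosing interval, so Q4W looks better than Q6W, and Q6W better than Q8W, when the true rates are equal.
- **Early stopping.** The distortion grows with the number of doses received, so completers and early stoppers are measured on different scales within one group.

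The treated spontaneous, traumatic and site-specific rates (secondary endpoints 1 to 3) have no formula of their own and would presumably inherit the error.

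**Working it through.** **Inputs, all from the protocol**

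- Interval τ: 28, 42 and 56 days (note to the primary endpoint).
- Doses in the treatment period (Overall Design): "The treatment period is 24 weeks, with Q4W, Q6W, and Q8W dosing intervals corresponding to 6, 4, and 3 doses, respectively".
- Extension (Overall Design): "allowing a maximum of 6, 4, and 3 additional doses, respectively", so at most k = 12, 8 and 6 doses in all.
- Ceiling (Dosage): "for a continuous treatment duration not exceeding 48 weeks", that is 48 × 7 = 336 days.
- Last scheduled dose of the treatment period (PK/PD sampling tables): D141, D127 and D113. With full extension, the day is 1 + (k − 1)τ: D309, D295 and D281.

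**Step 1. Reproduce the treatment period from the denominator**

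Denominator = (last dose day − first dose day) + τ = (k − 1)τ + τ = kτ.

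- Week 24: 140 + 28 = 126 + 42 = 112 + 56 = 168 days, exactly 24 weeks.
- Full extension: 308 + 28 = 294 + 42 = 280 + 56 = 336 days, exactly 48 weeks.

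The denominator is therefore sound and equals the whole treatment time in every group.

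**Step 2. Compare with the numerator window**

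The literal numerator covers τ days. At a constant bleeding rate, true ABR divided by reported ABR = kτ/τ = k, the number of doses given.

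| Group | Week 24: share of time counted | Factor | Full 48 weeks: share of time counted | Factor |
|---|---|---|---|---|
| Q4W (both doses) | 28/168 = 1/6 | 6 | 28/336 = 1/12 | 12 |
| Q6W | 42/168 = 1/4 | 4 | 42/336 = 1/8 | 8 |
| Q8W | 56/168 = 1/3 | 3 | 56/336 = 1/6 | 6 |

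**Step 3. Illustrate with one true rate in every group**

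Assume a true ABR of 8. This is the entry minimum of 4 bleeds in 6 months, annualised, and is not a prediction of treated bleeding on SR604. Reported ABR = 8/k.

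| Group | Week 24 | Full 48 weeks |
|---|---|---|
| Q4W | 8/6 = 1.33 | 8/12 = 0.67 |
| Q6W | 8/4 = 2.00 | 8/8 = 1.00 |
| Q8W | 8/3 = 2.67 | 8/6 = 1.33 |

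The Q8W-to-Q4W ratio at Week 24 is 2.67/1.33 = 2, and Q8W to Q6W is 2.67/2.00 = 1.33. Both come from the formula alone and do not depend on the assumed 8.

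**Step 4. Patients with no counted bleed**

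Under a Poisson assumption at the same rate, P(0) = exp(−8τ/365.25): 54% for Q4W, 40% for Q6W and 29% for Q8W. Truly bleed-free over 168 days: exp(−8 × 168/365.25) = 2.5%.

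**Step 5. After the correction**

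If the count covers the same days as the denominator, the factor is 1 and the formula returns 8.0 in every group at both time points.

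**The case against.** The strongest reply is that this is a drafting or translation slip and nobody would program it literally. The endpoint is named for Week 24 and for the total treatment period. The denominator fits only a count that runs from the first dose to the end of the interval after the last dose. Treated bleeds are to be documented throughout the treatment period, so the data will exist. On that reading there is no bias, and the SAP, to which the protocol leaves detailed methods, may define the count properly. This reading is very likely what was meant. It does not remove the problem: the same wording stands in four formulas that the protocol makes mandatory, and a SAP that counted differently would contradict the protocol on its primary endpoint.

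Some limits do stand:

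- The 12-fold figure needs Q4W, the total period and all 12 doses. A shorter extension or an early stop gives a smaller factor, down to 1 after a single dose.
- The two Q4W groups share one factor at equal dose counts, so the 0.2 versus 0.4 mg/kg contrast at Q4W is not tilted. The false ranking is between intervals.
- The protocol states no formal between-group hypothesis in this text, and it does not designate the all-bleed ABR as a key endpoint.
- The ABR of 8 rests on bleeding before the study, whether treated or not, whereas the primary endpoint counts treated bleeds on prophylaxis. The factors do not depend on it; the absolute rates and the zero-bleed percentages do.

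**Conclusion.** The concern holds. As written, the primary endpoint and secondary endpoint 4 do not measure an annualised bleeding rate over the stated period. The understatement equals the number of doses given: 6, 4 and 3 at Week 24 for Q4W, Q6W and Q8W, and at most 12, 8 and 6 over the total period. These figures assume completed dosing on schedule and a constant bleeding rate. If bleeding falls during treatment, the last interval is the quietest and the understatement is larger. Because this is the primary endpoint and the formula is binding, it must be corrected even though the intended meaning is easy to guess.

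**What to change.** In all four formulas, replace the numerator with the number of bleeding episodes (treated episodes for the primary endpoint) whose onset falls on or after the date of first dose and before the date of the last dose in the period plus the dosing interval. State that the treated spontaneous, traumatic and site-specific rates use the same window.

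The end date should be excluded. Counting D1 through D169 inclusive would be 169 days against a denominator of 168, an excess of 1/168 or about 0.6%, and D169 is also the first scheduled extension dose in every group.

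The cost is a one-sentence rewording in four places and matching SAP text and code. It needs no new data, visits or patients.

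### The ABR formulas count the full planned dosing interval after the last dose even for patients who leave the study before it ends, so unobserved days count as bleed-free

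*Protocol*

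**What the plan says.** Protocol, Efficacy Endpoints, Primary Efficacy Endpoint: the treated ABR, at Week 24 and over the total treatment period, "shall be calculated using the following formulas". In both formulas the denominator is the date of the last dose (for Week 24, the last within the 24 weeks) minus the date of the first dose, plus the dosing interval. A note makes that interval a constant by arm: "For the Q4W group, the dosing interval is 28 days", and "for the Q6W group, the dosing interval is 42 days; for the Q8W group, the dosing interval is 56 days". Secondary Efficacy Endpoint 4 repeats the formulas and the note for all bleeds, treated or not. None of the formulas has a term for study exit.

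Study Procedures, Follow-up Period, schedules the closing assessment "At Day 84 after the last dose or upon early withdrawal at any time", and bleeding events and their treatment are recorded there. Leaving before the last interval has run out is therefore foreseen. The Overall Design section extends follow-up to 84 days after the last dose in every arm.

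**The concern.** An annualized rate needs bleeds and days from the same observed window. A patient who leaves between the last dose and the end of the interval can add no more bleeds, yet the formula keeps the rest of the interval in the denominator. Those days are treated as observed and free of bleeding, so the expected ABR is always pulled down, in the drug's favour.

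The number of days that can be credited is set by the dosing interval, which is one of the features on which the arms differ. Two patients with the same bleeding and the same time on study can therefore get different ABRs purely because of their arm. With 6 patients per arm, one early exit can be visible in the primary endpoint.

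**Working it through.** **Inputs from the protocol.** Interval τ = 28, 42, 56 days (note to the primary endpoint). Doses in 24 weeks: 6, 4, 3 (Overall Design). Arm size: 6 (Sample Size). Follow-up: 84 days after the last dose (Overall Design). Assumptions: exit timing as stated in each step, doses on schedule, and a numerator that counts bleeds from the first dose onward.

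**Step 1: completers.** Denominator = (doses − 1) × τ + τ.
- Q4W: 140 + 28 = 168 days
- Q6W: 126 + 42 = 168 days
- Q8W: 112 + 56 = 168 days

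This reproduces the protocol's 24 weeks, so the formula is right for completers.

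**Step 2: exit t days after dose k.** Formula denominator = kτ. Observed time = (k − 1)τ + t. Credited but unobserved time = τ − t. The expected ABR is multiplied by [(k − 1)τ + t] / (kτ).

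With t = 14:

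| Exit 14 days after | Q4W | Q6W | Q8W |
|---|---|---|---|
| dose 1 | 14/28, understated 50% | 14/42, 67% | 14/56, 75% |
| dose 2 | 42/56, 25% | 56/84, 33% | 70/112, 38% |
| dose 3 | 70/84, 17% | 98/126, 22% | 126/168, 25% |

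One treated bleed in 14 observed days is 365.25/14 = 26.1 per year in any arm. The formula reports 365.25/28 = 13.0, 365.25/42 = 8.7 and 365.25/56 = 6.5.

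**Step 3: arm level.** One of six leaves 14 days after dose 1, five complete, and all have the same underlying rate.
- Mean of individual ABRs: (5 + 0.50)/6 = 0.917, (5 + 0.333)/6 = 0.889, (5 + 0.25)/6 = 0.875. The falls are about 8%, 11% and 12.5%.
- Pooled bleeds over pooled time: observed time is 5 × 168 + 14 = 854 days. The formula uses 868, 882 and 896 days. The falls are 1.6%, 3.2% and 4.7%.

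**Step 4: does the credited time rise with the interval?** Its upper bound is 28, 42 and 56 days. With exit spread evenly over days 1 to 167 after the first dose (an assumption), the mean credited time is 14.4, 21.4 and 28.3 days, and the mean factor on the ABR is 0.79, 0.74 and 0.69. On a given exit day the order can differ. At day 100 the formula denominators are 112 (Q4W), 126 (Q6W) and 112 (Q8W). Q6W is credited more than Q8W on days 42–55 and 84–111, which is 42 of 167 days, about 25%. Q8W is never credited less than Q4W.

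**The case against.** The best defence is that the affected group is narrow. Stopping treatment is not the same as leaving observation. Follow-up runs to 84 days after the last dose, longer than every interval, and bleeding is recorded through it. A patient who stops dosing but stays in follow-up has the whole interval observed. This stands: only full exit from the study before last dose plus interval causes the error, and it would be wrong to infer that every discontinuation does.

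Three other stronger readings are not supported:
- **Q8W is always the most favoured arm.** This holds at the maximum, on average and at equal time since the last dose, but not on every exit day (step 4).
- **Patients who leave because of bleeding get the largest percentage reduction.** The factor in step 2 depends only on exit time and interval. A higher bleeding rate enlarges the reduction in absolute ABR, not in percent.
- **Ongoing patients are affected at a data cut.** The protocol describes no interim analysis or cut-off, so this has no source.

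It can also be said that detailed methods are left to the SAP, which was not available for this review. That covers the choice of summary or model. It does not cover this formula, which the protocol makes mandatory: a SAP that cut the denominator at exit would depart from the protocol.

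Finally, the numerator as printed refers only to bleeds in the dosing interval after the last dose, while the denominator spans the whole period. Read literally, that mismatch affects completers too and is the larger defect. The per-patient figures for exit after dose 1 are the same under either reading, because the only interval is the last one. The later-dose and arm-level figures assume a numerator that covers the whole period.

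**Conclusion.** The point holds as a defect in a stated rule. The expected ABR is understated for any patient who leaves observation before last dose plus interval: by 50%, 67% and 75% (Q4W, Q6W, Q8W) for exit 14 days after dose 1, and by less after later doses. One such patient in six lowers the arm result by about 8% to 12.5% as a mean of individual ABRs, or 1.6% to 4.7% as a pooled rate. These arm-level figures assume an equal underlying bleeding rate and five completers.

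The longer-interval arms are favoured on average. A reader might infer that the between-arm comparison is biased by a known amount. It is not: the protocol gives no dropout rate, and if nobody exits inside the final interval the effect is zero. The correction should be made, but the endpoint does not fail for patients who are fully observed.

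**What to change.** In both the Week 24 and the total-period formulas, for treated bleeds and for all bleeds, end the window at the earlier of (a) last dose plus dosing interval and (b) the last date of bleed observation, that is, study exit. Count bleeds and days over that one window, starting at the first dose. Reword the numerator in the same edit so that it no longer refers only to the interval after the last dose.

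Completers keep 168 days at Week 24. A patient who leaves 14 days after dose 1 has 14 days in every arm instead of 28, 42 or 56.

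The cost is a change of protocol wording and the matching SAP code. The protocol does not state outright that an exit date is captured, but the early-withdrawal assessment records bleeding, so the date should be available. The downside is that ABRs of very early leavers become higher and less stable. Reporting total bleeds over total observed time per arm, next to the individual ABRs, deals with this. Any further modelling can stay with the SAP.
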